9.7 Leuprolide dose modifications guidelines

No dose modifications required.

9.8 Management of combined everolimus and EDT

Patients on everolimus + EDT who develop any grade 2 hematologic adverse event, grade 2 pulmonary toxicity or any other grade 3 non-hematologic toxicity (excluding hyperlipidemia) attributable to everolimus that warrants interruption of everolimus, may continue EDT. If everolimus or both EDT drugs must be completely discontinued, patient will be declared off treatment. In very special circumstances, study chair may allow continuation of everolimus or EDT pending the approval of the MSKCC IRB followed by the approval of the participating site's local IRB.

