 - Patients who are able to tolerate only leuprolide, but not letrozole, will undergo serum estradiol and testosterone testing at the start of every cycle. If serum estradiol remains within the post-menopausal range (females) or within the castration range (males), therapy on leuprolide will continue.

- Patients who are able to tolerate letrozole, but not leuprolide, will be removed from the study. In very special circumstances (ie. postmenopausal female patient) study chair may allow continuation of letrozole alone pending the approval of the local IRB.
- Treatment will continue until disease progression, global clinical deterioration, unacceptable toxicity and/or consent withdrawal.
- EDT may be held for a maximum of 4 weeks to recover from toxicity (see Sections 9.6 & 9.7).

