9.3 Part 1, Arm C: combined everolimus + EDT

- Day 1 of Cycle 1: Baseline serum estrone, estradiol, testosterone and follicle-stimulating hormone (FSH) level in all patients (if not already done). If estradiol is within postmenopausal range for women (≤ 30 pg/mL) and testosterone is within the castration range for men (≤ 50 ng/dL), patient does not have to have hormones retested at week 2 and maybe begin letrozole 2.5 mg po QD Week 2 of Cycle 1.
- Patients will begin leuprolide 7.5 mg IM and everolimus based on BSA:
 - Patients with a BSA $< 1.5 \text{ m}^2$ will receive everolimus 5 mg PO QD.
 - Patients with a BSA $\geq 1.5 \text{ m}^2$ will receive everolimus 7.5 mg PO QD.
- Week 2 of Cycle 1 (+/- 7 days): Women with estradiol not within postmenopausal range (≤ 30 pg/mL) or men with testosterone not within the castration range (≤ 50 ng/dL), measure serum estradiol and testosterone; if estradiol is within postmenopausal range for women or testosterone is within the castration range for men, begin letrozole 2.5 mg po QD. Otherwise, retest hormones on C2W1. Consult MSKCC PI if hormones are still not within range. to further discuss the letrozole start date.
- Leuprolide 7.5 mg IM will be given every 4 weeks (+/- 7 days).
- Everolimus and letrozole will be administered continuously using the same dose, schedule and administration instructions as outlined in sections 9.1 and 9.2. Patients will be given a pill diary to record the date and time that everolimus and letrozole were taken.
- One cycle of combined everolimus + EDT corresponds to 4 weeks of treatment.
- Everolimus, letrozole and leuprolide should be administered concurrently at all times. However, patients who are only able to tolerate everolimus and leuprolide, but not letrozole, can continue on therapy but need to undergo testing of serum estradiol and testosterone every 4 weeks. If serum estradiol remains within the post-menopausal range (in females) or castration range (males), therapy with leuprolide and everolimus continue.
 - Patients who are able to tolerate everolimus and letrozole, but not leuprolide, will be removed

from the study. In very special circumstances (ie. postmenopausal female patient), study chair may allow continuation of everolimus with letrozole pending the approval of the local IRB.

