9.5 Everolimus dose modifications and treatment interruptions/discontinuation guidelines

- Renal impairment: No dose adjustment necessary.
- Hepatic impairment: If total bilirubin $> 2 \text{ mg/dL}$, hold treatment for up to 4 weeks, then reduce dose to 5 mg PO daily once total bilirubin $\leq 2 \text{ mg/dL}$.
- Everolimus will be held for any grade 3 hematologic adverse event, grade 2 pulmonary toxicity or any other grade 3 non-hematologic toxicity, excluding hyperlipidemia.

- If recovery (grade 2 or less for hematologic or non-hematologic toxicities) occurs within 4 weeks, everolimus will be resumed at a reduced dose of 5 mg PO daily.
- Any grade ≥ 3 pulmonary toxicity occurring at any time during therapy warrants discontinuation of everolimus and the study chair should be contacted.
- If BSA changes by $> 10\%$ at any time during the study, the dose of everolimus must be adjusted if needed and accordingly.
- Everolimus will not be reduced below 5mg.
- Everolimus may be held for a maximum of 4 weeks from the scheduled date of cycle commencement to permit recovery from toxicities/adverse events as outlined above. If more than 4 weeks are required for recovery, the study chair may allow continuation of everolimus pending the approval of the local IRB.

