9.6 Letrozole dose modifications and treatment interruptions guidelines

If total bilirubin $> 3\text{mg/dL}$, hold treatment for up to 4 weeks, once total bilirubin $\leq 3\text{mg/dL}$, continue letrozole at 2.5 mg PO QD every other day.

Otherwise no modifications required.

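### Sections 9.8 and 9.5 give different hematologic grades for interrupting everolimus, and Sections 10 and 9.6 give opposite letrozole restart instructions at bilirubin between 2 and 3 mg/dL

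*Combined protocol and SAP*

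**What the plan says.** **Hematologic toxicity.** Section 9.5 is the everolimus hold rule: "Everolimus will be held for any grade 3 hematologic adverse event". It also sets the restart: "If recovery (grade 2 or less for hematologic or non-hematologic toxicities) occurs within 4 weeks, everolimus will be resumed at a reduced dose". Section 9.8 covers combined treatment. Its sentence starts "Patients on everolimus + EDT who develop any grade 2 hematologic adverse event", goes on to grade 2 pulmonary and other grade 3 non-hematologic toxicity, and ends "attributable to everolimus that warrants interruption of everolimus, may continue EDT".

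**Bilirubin.** Section 10 (summary of the evaluation plan during treatment) requires laboratory checks before treatment in weeks 1 and 3 of each cycle. Treatment goes ahead only if total bilirubin is at most 2 mg/dL and the count, renal and transaminase limits are met. If not, it is held and the patient is rechecked weekly. No drug or arm is named.

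Section 9.6, under the letrozole heading, starts a hold only above 3 mg/dL. Once bilirubin is back to 3 mg/dL or less, the instruction is to "continue letrozole at 2.5 mg PO QD every other day". It then says that nothing else needs modifying. Section 9.5 holds everolimus above 2 mg/dL and restarts it at 2 or less.

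**The concern.** These are working rules that four centers apply at the bedside. Section 9.8 repeats the grades in 9.5 for two kinds of toxicity and departs from them for the third. It therefore gives permission at a grade where 9.5 calls for no hold, and does not expressly give it at the grade where 9.5 does.

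The bilirubin rules matter more, because in one situation they give opposite instructions about the same drug on the same day. Arm B patients receive only letrozole and leuprolide, so in that arm the treatment Section 10 holds can only be EDT. Two sites following the protocol carefully could handle the same patient differently, and each would depart from one of the two sections.

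The situation is foreseeable in a liver cancer trial that admits patients with bilirubin up to 2 mg/dL, although the documents do not say how often it would arise.

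**Working it through.** No sample size, power or error rate is in question, so the check sets the rules side by side.

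**Step 1: hematologic trigger.**

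| Toxicity | 9.5: everolimus held | 9.8: EDT may continue |
|---|---|---|
| Hematologic | grade 3 | grade 2 |
| Pulmonary | grade 2 | grade 2 |
| Other non-hematologic, except hyperlipidemia | grade 3 | grade 3 |

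Two of the three grades agree; the hematologic one differs by one grade. Under 9.5, grade 2 is a level at which everolimus resumes. Section 9.8 applies only to events that warrant interrupting everolimus, and under 9.5 a grade 2 hematologic event does not. The entry therefore does nothing as written. If it were read as grade 2 or higher it would reach grade 3, but the text does not say so.

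**Step 2: bilirubin, Arm B.** The inputs are the Section 10 limit (2 mg/dL) and the 9.6 hold and restart limit (3 mg/dL). They disagree for bilirubin above 2 and up to 3 mg/dL, a width of 3 − 2 = 1 mg/dL.

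| Total bilirubin (mg/dL) | Section 10 | 9.6 (letrozole) | Relation |
|---|---|---|---|
| 2 or less, never higher | proceed | no change | agree |
| above 2 to 3, never above 3 | hold | no hold triggered | ambiguous |
| above 3 | hold | hold | agree |
| above 2 to 3, after a value above 3 | stay on hold until 2 or less | restart every other day | opposed |

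**Step 3: one patient.** In Arm B, bilirubin is 3.5 and then 2.5 mg/dL. At 3.5 both rules hold letrozole. At 2.5, 9.6 restarts it because 2.5 ≤ 3, while Section 10 keeps it held because 2.5 > 2.

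The 9.6 restart dose is 2.5 mg every 2 days: 2.5 / 2 = 1.25 mg/day, or 1.25 / 2.5 = 50% of the starting dose. This assumes that every other day overrides QD. If QD governs, the dose is 2.5 mg/day, so the range is 1.25 to 2.5 mg/day. Under Section 10 the dose is zero.

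**Step 4: is there a tie-breaker?** Section 10 does not refer to 9.5 to 9.8 at this point. It sends the reader to Section 11 for other adverse events, and Section 11 contains no hold rule. Section 9.2 sends Arm B sites to 9.6 and 9.7 for EDT holds, but does not say whether those sections take precedence over Section 10.

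**The case against.** The other side has a good deal to say, and several stronger readings fail.

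- **A reader might infer that 9.8 makes combined-treatment sites stop everolimus at grade 2, or stop EDT at grade 3.** It does neither. It is permissive and depends on an interruption that 9.5 decides. It also requires attribution to everolimus, which 9.5 does not. Section 9.3 refers Arm C holds to 9.5 through 9.8, and the closing line of 9.6 can be read as leaving letrozole unchanged. The entry is probably a drafting slip, and 9.5 itself says nothing about EDT.
- **A reader might infer from Section 9.3 that EDT cannot continue alone:** "Everolimus, letrozole and leuprolide should be administered concurrently at all times". The next sentence begins a set of exceptions, and 9.3 goes on to provide for holds. It is not a competing rule during a hold.
- **A reader might see contradictions wherever Section 10 holds and 9.6 does not,** as with a low count or a bilirubin that never passes 3 mg/dL. Saying that no modification is required does not forbid a hold required elsewhere. The heading of 9.6 does cover interruptions, so the text is unclear, but this is ambiguity.
- **A reader might set the renal stop in Section 10 against 9.5:** "Renal impairment: No dose adjustment necessary". Holding and then resuming at the same dose satisfies both.
- **In Arm C and Part 2, Section 10 could mean everolimus only,** since its bilirubin limit equals the one in 9.5. That reading is not available in Arm B, which has no everolimus.

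What survives is the wrong grade in 9.8 and the opposed restart instructions in Arm B. Applying the stricter limit throughout does not remove the second, because staying on hold at 2.5 mg/dL means not following 9.6.

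**Conclusion.** The concern holds for two thresholds. Section 9.8 is one hematologic grade away from 9.5, which leaves an entry with no effect and the grade 3 event not expressly covered. Sections 10 and 9.6 directly conflict on restarting letrozole in Arm B when bilirubin lies above 2 and up to 3 mg/dL after a hold above 3. For patients who enter that band without passing 3, the rules are ambiguous.

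This rests on two readings: that the hold in 9.6 means letrozole, which comes from its heading, and that Section 10 applies to every arm, since it makes no exception.

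A reader might go further and infer bias in progression-free survival at 6 months (PFS6). Section 13 makes a delay of more than 4 weeks a ground for removal, and Section 14 counts coming off study before the 6-month scan as an event. The documents do not support a claim of that kind. They give no rate for such holds, the 4-week limit in 9.2 refers to 9.6 and 9.7 and does not mention Section 10, and Section 13 lets the study chair allow continuation subject to local IRB approval. No effect on PFS6, power or everolimus dose is claimed. The point is worth correcting because it concerns consistent and safe dosing.

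**What to change.** 1. In 9.8, change the hematologic entry from grade 2 to grade 3.
2. In Section 10, state that the 2 mg/dL bilirubin limit applies to everolimus and that letrozole follows 9.6 (hold above 3, restart at 3 mg/dL or less). If the clinical team wants letrozole held above 2 mg/dL, change both limits in 9.6 to 2 mg/dL instead.
3. Leave the count, renal and transaminase stops in Section 10 as they are in all arms unless the clinical team decides otherwise. Limiting them to everolimus would remove them from Arm B altogether, which is a clinical choice and goes beyond an editorial correction.
4. In 9.6, give the restart dose as 2.5 mg every other day and delete QD.

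The cost is a short protocol amendment with IRB approval. It needs no extra visits, tests or form fields.

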9.9 Ancillary medications/therapies

- Primary prophylactic G-CSF may be given as indicated.
- Anti-emetic therapy will be provided according to institutional guidelines.
- Erythropoietin and/or transfusions may be given according to institutional guidelines or investigator preference.
- Add back therapy with norethindrone acetate 5 mg PO QD will be initiated after 6 months of EDT in females < 18 years old.

MEMORIAL SLOAN-KETTERING CANCER CENTER IRB PROTOCOL

IRB#: 11-211 A(6)

- Calcium and vitamin D supplementation will be given according to the National Osteoporosis Foundation (NOF; www.nof.org) guidelines given the risk of decreased bone mineral density with EDT.
 - Calcium: 1000 mg/day for children and adults < 50 years old; 1200 mg/day for adults \geq 50 years old. This represents total intake from supplements and food.
 - Vitamin D: 400 IU/day for children; 400-800 IU/day for adults < 50 years old; 800-1000 IU/day for adults \geq 50 years old; maximum safe dose is 4000 IU/day total intake from supplements and food. Vitamin D2 (ergocalciferol) and D3 (cholecalciferol) are both acceptable.
 - Patients will be provided with a pill diary to record the date and time that calcium and vitamin D are taken.

10.0 EVALUATION DURING TREATMENT/INTERVENTION

Treatment/Intervention	Anytime before C1D1	Within 4 wks of Tx	Within 2 wks of Tx	C1D1 ^a	C1W2 ^y	C1W3 ^f	C2W1 onwards ^b	C2W3 onwards ^b	Q4 wks	Q12 wks	4 wks after study
Study therapy											
Everolimus POQD ^c				x				Continuous administration			
Leuprolide 7.5 mg IM				x					x ^d		
Letrozole 2.5 mg PO QD					x ^e			Continuous administration			
Clinical											
History, physical exam, vitals, weight, ECOG versus Lansky as applicable, BSA			x		x ^v	x ^f	x	x ^f			x
Adverse event assessment				x	x ^v	x ^f	x	x ^f			x
Laboratory											
CBC +differential, metabolic panel ^g , Ca ²⁺ , PO ₄ , liver function tests ^h , LDH			x			x ^f	x ⁱ	x ^{i,f}			x
Ammonia ^w			x ^w	x ^w	x ^w	x ^w	x ^w	x ^w	x ^w	x ^w	x ^w
Hepatitis B sAg, cAb; +		x									
Quantitative PCR for hepatitis C and hepatitis B, (if known infection)			x ^j							x ^j	
Fasting glucose and lipid profile ^k			x			x ^l					x
Serum estrogens, testosterone, FSH			x	X ^{d,m,n}					x ^o	x	
Plasma neuropeptides, transcobalamin, DCP, AFP			x						x ^o		
Urinalysis ^p			x								
Serum pregnancy test			x ^q								
Imaging											
CT chest/abdomen/pelvis with contrast and triphasic liver ^r		x							x ^s		

MEMORIAL SLOAN-KETTERING CANCER CENTER
 IRB PROTOCOL

IRB#: 11-211 A(6)

Treatment/Intervention	Anytime before C1D1	Within 4 wks of Tx	Within 2 wks of Tx ^a	C1D1 ^a	C1W2 ^v	C1W3 ^f	C2W1 onwards ^b	C2W3 onwards ^b	Q4 wks	Q12 wks	4 wks after study
Other											
Blood sample for future research			x								
Pathology specimen ^t	x			Repeat if patient undergoes surgery							
Bone mineral density scan (patients \geq 16 years old)		x		Annually							
Bone age (all patients 12-15 yrs old) ^u		x		Every 6 months							
EKG			x	As clinically indicated							
Pulmonary function tests				As clinically indicated							
Psychiatric evaluation				As clinically indicated							

^a C1D1 = cycle 1 day 1; C1W2 = cycle 1 week 2

^b Continue same for all subsequent cycles

^c Patients with BSA $< 1.5 \text{ m}^2$ receive everolimus 5 mg PO QD. Patients with BSA $\geq 1.5 \text{ m}^2$ receive everolimus 7.5 mg PO QD. If BSA changes by $> 10\%$ above or below the 1.5 m^2 cut-off at any time during the study, the dose of everolimus must be adjusted accordingly.

^d May be done +/- 7 days

^e If estradiol (females) and testosterone (males) are within castration range. Otherwise, delay start of letrozole until week 4, coinciding with 2nd dose of leuprolide.

^f In exceptional circumstances, which must be approved by the MSKCC principal investigator, week 3 visit can be schedule with a local oncologists along with the week 3 bloods

^g Includes Na, K, Cl, HCO₃, BUN, creatinine, glucose, AST, ALT, alkaline phosphatase.

^h Total and direct bilirubin, albumin. INR/PT/PTT is required at screening. For weeks 1 and 3 of each cycle, only PT/INR is required.

ⁱ To be repeated during weeks 1 and 3 of every cycle.

^j Only if Hepatitis B and/or C screening serologies are positive

^k Total cholesterol, triglycerides, LDL and HDL

^l To be repeated during week 1 of every cycle.

^m For patients on EDT, serum estradiol and testosterone only (FSH and estrone excluded). The post menopausal cutoff level for serum estradiol is $\leq 30 \text{ pg/mL}$. See sections 9.2, 9.3, or 9.4 for further clarification.

ⁿ For patients on EDT, the castration cutoff for testosterone is $< 50 \text{ ng/dL}$. See sections 9.2, 9.3, or 9.4 for further clarification.

^o For patients on EDT, may be performed at same time as other blood draws on C4W1, C7W1, C10W1, etc.

^p Includes specific gravity, color, turbidity, pH, albumin, glucose, ketones, bilirubin, blood, urobilinogen, leucocyte esterase, nitrite, and other findings

^q To be completed within 7 days of starting study therapy.

^r Or MRI abdomen/pelvis and non-contrast enhanced CT chest if patient allergic to CT contrast dye despite pre-medication, or other clinical contraindication.

^s Imaging studies performed at 6 months (+/- two weeks) will be used to determine the primary endpoint (PFS6)

MEMORIAL SLOAN-KETTERING CANCER CENTER
IRB PROTOCOL

IRB#: 11-211 A(6)

^tTumor aromatase and estrogen receptor expression, Ki67, and markers of mTOR activity (phospho-S6 kinase, phospho-Akt, cyclin D1) on biopsy specimens obtained before joining the study. For patients who undergo surgery on protocol therapy, tissue will be reexamined for same markers.

^u Left hand and wrist radiographs using the Greulich-Pyle Atlas.

^v If patient is randomized to Arm A, the Cycle 1 Week 2 visit can be scheduled with a local oncologist upon approval by the MSKCC principal investigator in exceptional circumstances.

^wAmmonia testing should be tested within 2 weeks before or on Cycle 1 Day 1 and at every visit when blood work is required.

Summary of evaluation plan during treatment

- Patients will undergo clinical and laboratory evaluations on weeks 1, 2 and 3 of Cycle 1. For all subsequent cycles starting with Cycle 2, evaluations will take place on weeks 1 and 3.
- Only clinical and laboratory assessments performed at Memorial Sloan Kettering Cancer Center or participating sites will be used to determine if patient will proceed with protocol treatment using the parameters listed below. Protocol assessments performed at a local oncologist may be used to determine treatment decisions at discretion of treating investigator and local oncologist.
- Before treatment on week 1 and 3 of each cycle: CBC and differential, comprehensive metabolic panel (Na, K, Cl, HCO₃, BUN, creatinine, AST, ALT, alkaline phosphatase, glucose), LDH, calcium, phosphorus, albumin, bilirubin, PT/INR, and ammonia. Treatment will only proceed if:
 - Hematologic: ANC $\geq 1.0 \times 10^9/L$, platelets $\geq 50 \times 10^9/L$
 - Renal: creatinine $\leq 2 \times$ upper limit of normal or creatinine Clearance of $\geq 60 \text{ cc/mL}/1.73 \text{ m}^2$ for patients > 16 years old. For patients ≤ 16 years of age, creatinine Clearance of $\geq 70 \text{ cc/mL}/1.73 \text{ m}^2$ or serum creatinine based on the following chart:

Creatinine clearance or radioisotope GFR $\geq 70 \text{ ml/min}/1.73 \text{ m}^2$ or serum creatinine based on age/gender as follows:

Age	Maximum Serum Creatinine (mg/dL)	
	Male	Female
10 to < 13 years	1.2	1.2
13 to < 16 years	1.5	1.4
≥ 16 years	1.7	1.4

The threshold creatinine values in this Table were derived from the Schwartz formula for estimating GFR (Schwartz et al. J. Peds, 106:522, 1985) utilizing child length and stature data published by the CDC.

- Hepatic: total bilirubin $\leq 2 \text{ mg/dL}$, alanine and aminotransferase levels $\leq 5 \times$ upper limit of normal for age.
- If hematologic, renal and hepatic function criteria are not met, treatment will be held and the patient will be reassessed weekly. Please refer to section 11.0 Toxicities/Side Effects for the

management of other adverse events during therapy.

- Fasting blood glucose and fasting lipid profile (total cholesterol, triglycerides, LDL, HDL) will be drawn on week 1 of each cycle beginning with cycle 2.
- Past FLL-HCC patients have also been referred for psychiatric services with depressive symptoms, immaturity and suicidal ideation as the most commonly observed symptoms. Participants on study will be psychiatrically evaluated as clinically indicated.

Follow-up after study therapy

Patients who have discontinued the study will be asked to return four weeks later for an exit visit consisting of a medical history, vital signs, physical examination, toxicity check and blood tests including a complete blood count, Na, K, Cl, HCO₃, BUN, creatinine, glucose, AST, ALT, INR/PT/PTT, Ca, Mg, phosphorus, alkaline phosphatase, LDH, fasting blood glucose, fasting lipid panel, and ammonia. Patients who were on EDT will also be asked to provide blood to test serum estrogens, testosterone and FSH. After this exit visit, patients may be contacted every 3 months to monitor their survival. This information may also be checked through medical records or updated mortality lists of the institutions. Patients will also be encouraged to continue with periodic imaging after they have completed the study.

Correlative studies

Correlative studies are particularly important for rare diseases like FLL-HCC, and can be used to enhance the quantity and quality of information obtained from this study. Serum and tissue biomarker studies will be correlated with study outcomes to determine if they may have any predictive or prognostic value. Changes in biomarker expression in post-treatment specimens will also provide information about the precision of therapeutic targeting.

All specimens, including those procured at UCSF, JHU and DF/BWCC/MGHCC will be shipped to MSKCC or Labcorp and will be analyzed where the sample is sent.

- **Tissue biomarker analysis**

Tissue procurement and processing

- During screening, a block(s) of archived formalin-fixed paraffin-embedded FLL-HCC tumor tissue will be collected prior to the study and will be sent to the central laboratory facility at MSKCC along with the corresponding pathology report. Alternatively, approximately 20 unstained slides (if available) will be sent.
- Adequate samples should be sent to the pathology core lab facility at MSKCC, preferably within 4 weeks of beginning the study to permit adequate time to evaluate the samples and determine if additional samples are required.

MEMORIAL SLOAN-KETTERING CANCER CENTER IRB PROTOCOL

IRB#: 11-211 A(6)

- **For MSKCC patients:** samples are to be sent to the attention of [name], Department of Pathology, [name].
- **For participating sites:** samples are to be sent to the attention of Study 11-211, [name], [name].
- The tumor block should be carefully selected by a pathologist or a skilled, experienced histology associate and should include a deep diagnostic section containing generous tumor tissue.
- If the adequacy of the tumor specimen is unclear, it is acceptable to submit more than 1 block or series of slide replicates containing tumor tissue. These must be accompanied by the pathology report, otherwise the submission will be considered incomplete.
- If insufficient tumor is available to perform biomarker analysis, patients will be offered the opportunity to undergo a repeat biopsy to obtain an adequate sample.
- Tumor slides taken from the tumor block to be submitted to the MSKCC core laboratory facility should be prepared according to the following preferred specifications:
 - Approximately 20 slides in 5 micron thick slices should be cut from the same block onto the charged slides.
 - The slides should be labeled by etching or using an indelible histology marker with the block ID number to match the pathology report.
- Subject identifiers (e.g. name, social security number) should be blacked out on the pathology report to protect subject identity. However, the subject ID number should be written on the report. The specimen collection date and block ID numbers should be visible and legible.
- No additional invasive procedures to obtain tumor tissue are required for this study. However, if a patient undergoes surgery or another biopsy during the study as part of the routine investigations of the subject's disease, a fresh formalin-fixed paraffin-embedded tumor tissue sample (block or unstained slides) may be submitted of the central laboratory for additional immunohistochemical analysis.
- Participating sites will notify the Multicenter Trial Research Staff at MSKCC or [contact]) when samples are shipped by using a sample requisition form. The Research Staff will contact the receiving laboratory to confirm receipt of the specimens. In addition to the information noted above, the following information will be recorded: (1)MSKCC CRDB protocol participant #, (2) patients initials, (3) sample type (slides or block), (4) date specimen was obtained, (5) shipping date.

Immunohistochemical analysis

- Immunohistochemical analysis will be performed on formalin-fixed paraffin embedded tumor specimens. Tumors will be assayed at baseline using monoclonal antibodies to stain for:
 - Aromatase
 - Estrogen receptor expression
 - Ki67
 - Phospho-S6 (phosphorylated ribosomal protein S6)
 - Phospho-Akt
 - Cyclin D1
- Evaluation of the tumor specimens and description of staining intensity will be performed by [name].
- The baseline staining pattern for the various markers will be correlated with progression-free survival at 6 months (PFS6).
- Immunostains will be repeated on tumor specimens obtained from patients who undergo surgery on protocol therapy. Changes in tissue biomarkers from baseline to surgery will be summarized descriptively.

Blood biomarkers

Blood samples for future research

- Two tubes of blood for plasma and serum to be used in future research studies at MSKCC will be collected from all patients
 - Kits for these samples will be provided to each participating site by MSKCC and collected plasma and serum samples will be bulk shipped to MSKCC every six months.
 - Instructions for processing these samples, as well as shipment information, are in the Lab Manual.

Putative FLL-HCC tumor biomarkers to be measured within 2 weeks of initiating study therapy and every 12 weeks during the protocol in all patients.

- **AFP**
 - AFP will be collected and resulted at respective site's laboratory.
- **Plasma neurotensin**
 - **Patients should be fasting 10 - 12 hours prior to collection of specimen. Patients should not be on any antacid medication or medications that affect gastroentero-intestinal function, if possible, for at least 48 hours prior to collection.**
 - A 10mL sample will be drawn into an EDTA z top tube provided by the Interscience Institute through LabCorp. The serum should be separated from the whole blood as soon as possible to maintain the integrity of the sample. Once the serum has been

MEMORIAL SLOAN-KETTERING CANCER CENTER IRB PROTOCOL

IRB#: 11-211 A(6)

separated it should be frozen immediately until the sample is ready to be shipped. All neurotensin samples will be processed at Inter Science Institute [name]. Further details regarding sample preparation, packaging, and shipping are found in the study lab manual.

- **Serum unsaturated vitamin B12 binding capacity (transcobalamin)**
 - **Must draw before Schilling test, transfusions, or B₁₂ therapy is started.**
 - A 0.5 mL sample will be drawn into a red-top, gel-barrier, or EDTA tube provided by LabCorp. The serum should be separated and put into a plastic transfer tube and frozen immediately until it is ready to be shipped. All unsaturated vitamin B12 binding capacity samples will be processed at LabCorp [name]. Further details regarding sample preparation, packaging, and shipping are found in the study lab manual.
- **Serum des-γ-carboxyprothrombin (DCP)**
 - No special patient preparations are necessary.
 - A 2 mL sample will be drawn into a red-top or gel-barrier tube provided by LabCorp. The serum should be separated, put into a plastic transfer tube, and frozen immediately until it is ready to be shipped. All unsaturated serum DCP samples will be processed at LabCorp [name]. Further details regarding sample preparation, packaging, and shipping are found in the study lab manual.

Serum hormones

- All serum hormones will be processed and resulted at the respective site they were drawn at. Patients on the EDT-containing study arms (Arms B and C) will have blood drawn for the following serum hormones:
 - Serum estrone
 - Serum estradiol
 - Serum follicle stimulating hormone (FSH)
 - Serum testosterone
- Serum hormones will be measured within 2 weeks of initiating study therapy. Serum estradiol and testosterone will be measured again during Week 2 of therapy if required per protocol. All hormones (estrone, estradiol, FSH, testosterone) will be measured every 12 weeks thereafter.

• Sample storage and destruction

Blood and tumor samples collected for biomarker analysis and any other components from the cells may be stored for up to 20 years for future scientific investigations related to FLL-HCC. Study subjects maintain the right to have the sample material destroyed at any time by contacting the principal investigator. MSKCC will be the exclusive owner of any data, discoveries or derivative materials from the sample materials and is responsible for the destruction of the sample(s) at the request of the research subject through the principal investigator, at the end of the storage period, or as appropriate (e.g. the scientific rationale for experimentation with a certain sample type no longer

justifies keeping the sample). The principal investigator will provide MSKCC with the required study and subject numbers so that any remaining blood and tumor samples and any other cell components can be located and destroyed.

